5.3.1. Binary Endpoint

For the binary response endpoints (eg, SDAI remission rates), subjects with missing values will be handled by:

- non-responder imputation (NRI) method, ie, setting any missing values to be non-responsive (0).
- will be used as observed (ie, excluding any missing values from analysis).

5.3.2. Continuous Endpoints

For non-patient reported outcome variables, the missing values will be handled as following:

- For continuous endpoints measured longitudinally, the missing values post-baseline will be handled in a linear mixed-effect model with repeated measures for this continuous variable, where the values are assumed to be missing at random.
- For the continuous endpoint not measured longitudinally, the post-baseline missing values will be:
 - as observed (ie, excluding any missing values from analysis);
 - imputed using last observation carried forward (LOCF).

For PRO endpoints, rules suggested by the developers of these PROs will be followed in calculating the values of a given component at a scheduled assessment. If these rules are not enough for imputing a value, then the missing values will be handled in the same way as non-patient reported outcome variables.

6. ANALYSES AND SUMMARIES

6.1. Primary Endpoint(s)

The primary efficacy analysis will be conducted on SDAI change from baseline at Week 12. Analysis will include data on PF-06650833 (400, 200, 60, 20 mg, QD) and placebo arms.

6.1.1. Primary Analysis

The primary analysis will be based on the Bayesian analysis outlined in [Appendix 4](#). The Bayesian analysis will be based on ITT population set.

6.1.2. Sensitivity/Robustness Analyses

There are 3 sets of analyses.

Set 1:

The sensitivity analysis will be based sensitivity prior models on the Bayesian analysis outlined in [Appendix 4](#). The Bayesian analysis will be based on ITT population set.

Set 2:

- Population set
 - ITT;
 - PP.
- Missing data imputation
 - Observed;
 - LOCF.
- ANCOVA (see [Section 5.2.2](#))
 - Baseline SDAI as a covariate;
 - Baseline SDAI and previous anti-TNF use as covariates.

Set 3:

- Population set:
 - ITT;
 - PP.
- Missing data imputation – none (Observed);
- MMRM (see [Section 5.2.2](#)) for analysis of change from baseline in SDAI at Weeks 4, 8, and 12:
 - Baseline SDAI as a covariate;
 - Baseline SDAI and previous anti-TNF use as covariates.

6.2. Secondary Endpoint(s)

6.2.1. SDAI

Analysis of number of subjects with SDAI remission ($SDAI \leq 3.3$) and SDAI low disease activity ($SDAI \leq 11$) at Weeks 4, 8, and 12:

- ITT population set;
- Missing data imputation:
 - Observed;
 - NRI.
- Normal approximation.

Analysis of change from baseline in SDAI at Weeks 4, 8, and 12:

- ITT population set;

- Missing data imputation – none (Observed);
- MMRM.

6.2.2. DAS

For DAS28-3 (ESR), DAS28-3 (CRP), DAS28 -4 (ESR), and DAS28-4 (CRP), analysis of number of subjects with DAS28 remission (DAS <2.6) and DAS28 low disease activity (DAS28 <3.2) at Weeks 4, 8, and 12:

- ITT population set;
- Missing data imputation:
 - Observed;
 - NRI.
- Normal approximation.

Analysis of change from baseline in DAS28-3 (ESR), DAS28-3 (CRP), DAS28 -4 (ESR), and DAS28-4 (CRP) at Weeks 4, 8, and 12:

- ITT population set;
- Missing data imputation – none (Observed);
- MMRM.

6.2.3. ACR

Analysis of ACR20, ACR20, and ACR50 rates at Weeks 4, 8, and 12:

- ITT population set;
- Missing data imputation:
 - Observed;
 - NRI.
- Normal approximation.

6.2.4. hsCRP

Analysis of change from baseline in hsCRP at Weeks 4, 8, and 12:

- ITT population set;
- Missing data imputation – none (Observed);
- MMRM.

6.2.5. Tender/Painful and Swollen Joint Count

Analysis of change from baseline in the Tender/Painful and Swollen Joint Count (28) at Weeks 4, 8, and 12:

- ITT population set;
- Missing data imputation – none (Observed);
- MMRM.

6.2.6. PhGA of Arthritis

Analysis of change from baseline in PhGA of arthritis at Weeks 4, 8, and 12:

- ITT population set;
- Missing data imputation – none (Observed);
- MMRM.

6.3. PRO Endpoints

Analysis of change from baseline in for outcomes research endpoints at Weeks 4, 8, and 12:

- Endpoints are PAAP VAS, PtGA VAS, and HAQ-DI;
- ITT population set;
- Missing data imputation – none (Observed);
- MMRM.

Analysis of change from baseline in for outcomes research endpoints at Week 12:

- Endpoints:
 - SF-36v.2 (acute) 8 domain scores, PCS, and MCS;
 - EQ-5D-3L score;
 - FACIT-F total score.
- ITT population set;
- Missing data imputation – none (Observed);
- MMRM.

CCI [REDACTED]
[REDACTED]
[REDACTED]

- CCI [REDACTED]
- [REDACTED]
- [REDACTED]
- [REDACTED]
- [REDACTED]
- [REDACTED]
- [REDACTED]
- [REDACTED]

6.5. Subset Analyses

Summary statistics for the SDAI endpoints will be presented by baseline smoking status and by previous anti-TNF use.

6.6. Baseline and Other Summaries and Analyses

6.6.1. Baseline Summaries

Demographics and medical history variables as defined in [Section 3.5](#) will be summarized by treatment group.

6.6.2. Study Conduct and Subject Disposition

Subject evaluation groups will show end of study subject disposition and will show which subjects were analyzed in the ITT, PP, and SAF analysis sets. Frequency counts will be supplied for subject discontinuations by treatment.

Data will be reported in accordance with Pfizer reporting standards.

6.6.3. Study Treatment Exposure

A summary of compliance by visit and treatment group will be provided.

6.6.4. Concomitant Medications and Non-Drug Treatments

All concomitant medication(s) as well as non-drug treatment(s) will be provided in the listings.

6.7. Safety Summaries and Analyses

Safety analysis will be based on the SAF analysis set. The summary will be done for:

- PF-06650833 (400, 200, 60, 20 mg, QD) and placebo;
- PF-06650833 (400, 200, 60, 20 mg, QD), tofacitinib, and placebo.

All clinical AEs, serious adverse events (SAEs), treatment-emergent signs and symptoms (TEAEs), withdrawal due to AEs, ECGs, vital signs and safety laboratory data will be reviewed and summarized on an ongoing basis during the study to evaluate the safety of subjects.

Safety data will be presented in tabular and/or graphical format and summarized descriptively, where appropriate. All safety endpoints will be listed and summarized in accordance with Pfizer Data Standards. Categorical outcomes (eg, AEs) will be summarized by subject counts and percentage. Continuous outcome (eg, blood pressure, pulse rate, etc) will be summarized using N, mean, median, standard deviation, etc. Change from baseline in laboratory data, ECGs and vital signs will also be summarized. Subject listings will be produced for these safety endpoints accordingly.

6.7.1. Adverse Events

It should be recognized that most studies are not designed to reliably demonstrate a causal relationship between the use of a pharmaceutical product and an adverse event or a group of adverse events. Except for select events in unique situations, studies do not employ formal adjudication procedures for the purpose of event classification. CCI

[REDACTED]

[REDACTED]

Nominal p-values (Tier-1 events only) and 95% confidence intervals (Tier-1 and Tier-2 events) will be provided for between treatment differences in the percentage of patients with events. Reporting p-values and confidence intervals will follow Pfizer standards.

6.7.2. Laboratory Data

Laboratory data will be listed and summarized by treatment and visit in accordance with the Pfizer reporting standards.

6.7.3. Vital Signs

Absolute values and changes from baseline in systolic and diastolic blood pressure, respiratory rate, pulse rate and temperature will be listed summarized by treatment and visit in accordance with the Pfizer reporting standards.

6.7.4. Electrocardiogram

Categorical summary tables will be summarized by treatment and visit using Pfizer reporting standards. A listing of ECG comments on findings and normal/abnormal results will be provided.

6.7.5. Physical Examination

All physical exam data will be provided in the listings.

7. INTERIM ANALYSES

At least one interim analysis (IA) for futility may be performed. The final number and timing of the IA(s) will be defined by the sponsor, but preliminarily one may be conducted at approximately 6 months after the randomization of the first subject and/or after at least 50% of the planned subjects, ie, approximately 100 subjects, completed the twelve week active treatment phase.

The futility analysis of SDAI change from baseline at Week 12 will be utilizing the Bayesian framework outlined in [Appendix 4](#). Noninformative prior distribution model for the placebo arm, outlined in [Appendix 4](#), will be used for the interim analysis data. The futility might be declared if the posterior probability of the treatment effect being greater than zero is less than 10% for all the active arms.

The interim analysis will not have an option to stop the trial early for efficacy.

9. APPENDICES

Appendix 1: Summary of Efficacy Analyses

Primary Efficacy Endpoint	Statistical Method	Missing Data
Change from baseline in SDAI at Week 12	ANCOVA with baseline SDAI as a covariate	Observed
Change from baseline in SDAI at Week 12	ANCOVA with baseline SDAI as a covariate	LOCF
Change from baseline in SDAI at Week 12	ANCOVA with baseline SDAI and anti-TNF use as covariates	Observed
Change from baseline in SDAI at Week 12	ANCOVA with baseline SDAI and anti-TNF use as covariates	LOCF
Change from baseline in SDAI at Week 12	Bayesian analysis of posterior distributions of the SDAI scores and placebo adjusted change from baseline	-

Note: Populations (ITT, PP); Treatment Groups (PF-06650833, placebo)

Secondary Efficacy Endpoints	Statistical Method	Missing Data
SDAI remission and low disease activity scale at Weeks 4, 8, and 12	Normal approximation	Observed
SDAI remission and low disease activity scale at Weeks 4, 8, and 12	Normal approximation	NRI
DAS28-3 (ESR), DAS28-3 (CRP), DAS28 -4 (ESR), and DAS28-4 (CRP) remission and low disease activity scale at Weeks 4, 8, and 12	Normal approximation	Observed
DAS28-3 (ESR), DAS28-3 (CRP), DAS28 -4 (ESR), and DAS28-4 (CRP) remission and low disease activity scale at Weeks 4, 8, and 12	Normal approximation	NRI
Change from baseline in SDAI at Weeks 4, 8, and 12	MMRM	Observed

090177e190fc4501\Approved\Approved On: 27-May-2019 06:05 (GMT)

Secondary Efficacy Endpoints	Statistical Method	Missing Data
Change from baseline in DAS28 (eg, DAS28-3 (ESR), DAS28-3 (CRP), DAS28 -4 (ESR), and DAS28-4 (CRP)) at Weeks 4, 8, and 12	MMRM	Observed
ACR20, ACR50, and ACR70 at Weeks 4, 8, and 12	Normal approximation	Observed
ACR20, ACR50, and ACR70 at Weeks 4, 8, and 12	Normal approximation	NRI
Change from baseline in hsCRP at Weeks 4, 8, and 12	MMRM	Observed
Change from baseline in in the Tender/Painful and Swollen Joint Count (28) at Weeks 4, 8, and 12	MMRM	Observed
Change from baseline in PhGA of Arthritis at Weeks 4, 8, and 12	MMRM	Observed

Note: Populations (ITT); Treatment Groups (PF-06650833 and placebo)

090177e190fc4501\Approved\Approved On: 27-May-2019 06:05 (GMT)

Appendix 2: Details of Visit Windows

Visit windows will be used for efficacy variables, and for any safety data that display/summarize by study visit. For other endpoints (eg, ECG, vital signs), visit windows will be applied for summary statistics by study visits if required.

Visit Label	Target Day	Definition [Day window]
Screening		Days -28 to Day 0
Baseline	Day 1, Baseline	Day 1
Week 1	8	Days 2 to 15
Week 4	29	Days 16 to 36
Week 6	43	Days 37 to 50
Week 8	57	Days 51 to 64
Week 10	71	Days 65 to 78
Week 12	85	Days 79 to 92
Follow Up/End of Study		
Week 14	99	Days 93 to 106
Week 16	113	Days 107 to -

For the lab values, if the calculated study day for the labelled baseline visit is not study Day 1, but falls within 40 days before the start of the study dosing, then that data should be used for the baseline instead of leaving baseline missing.

For the other values, if the calculated study day for the labelled baseline visit is not study Day 1, but falls before the start of the study dosing, then that data should be used for the baseline instead of leaving baseline missing.

If two or more visits fall into the same window, keep the one closest to the Target Day. If two visits are equaled distant from the Target Day in absolute value, the later visit should be used.

Safety analysis may follow Pfizer standard.

090177e190fc4501\Approved\Approved On: 27-May-2019 06:05 (GMT)

Appendix 3: Data Derivation Details

A patient is said to have achieved the ACR20 criteria⁺ when all of the following bulleted points are true:

- A 20% improvement from baseline in the tender/painful joint count (TCJ28).
- A 20% improvement from baseline in the swollen joint count (SJC28).
- A 20% improvement from baseline in *at least 3* of the following 5 variables:
 1. PhGA of Arthritis VAS;
 2. PAAP VAS;
 3. PtGA of Arthritis VAS;
 4. HAQ disability index;
 5. Results of ESR or CRP blood test (both of which test for inflammation).

ACR50 and ACR70 are defined analogously.

There are many forms of the DAS. The DAS used in this study is the DAS using the 28-count subsets of tender/painful joints and swollen joints, together with either CRP or ESR, to derive the DAS28-3 (CRP), DAS28-4 (CRP), or DAS28-3 (ESR) and DAS28-4 (ESR), which are calculated using the following formulae, respectively:

$$\text{DAS28-4(ESR)} = (0.56 * \sqrt{\text{TJC28}}) + 0.28 * \sqrt{\text{SJC28}} + 0.70 * \ln(\text{ESR}) + 0.014 * \text{GH}$$

$$\text{DAS28-3(ESR)} = [0.56 * \sqrt{\text{TJC28}} + 0.28 * \sqrt{\text{SJC28}} + 0.70 * \ln(\text{ESR})] * 1.08 + 0.16$$

$$\text{DAS28-4(CRP)} = 0.56 * \sqrt{\text{TJC28}} + 0.28 * \sqrt{\text{SJC28}} + 0.36 * \ln(\text{CRP}+1) + 0.014 * \text{GH} + 0.96$$

$$\text{DAS28-3(CRP)} = [0.56 * \sqrt{\text{TJC28}} + 0.28 * \sqrt{\text{SJC28}} + 0.36 * \ln(\text{CRP}+1)] * 1.10 + 1.15$$

where TJC28 is number of painful joints out of 28 joints, SJC28 is number of swollen joints out of 28 joints, GH is the general health or patients' global assessment of disease activity on a 100 mm VAS, ln is the natural logarithm, ESR is in mm/first hour, and CRP is in mg/L.

Handling Missing Joint Counts:

- A missing painful/tender assessment or one NOT DONE at *baseline* is set to “not painful/tender”;
- A missing swollen assessment or one NOT DONE at *baseline* is set to “not swollen”;
- A missing painful/tender assessment or one NOT DONE *post baseline* is set to “painful/tender”;

- A missing swollen assessment or one NOT DONE at *post baseline* is set to “swollen”.

Note that joints marked NOT APPLICABLE are not to be counted in the summation of swollen and painful/tender joints at baseline and post baseline.

Any *new* NOT APPLICABLE for a joint POST BASELINE is set to “painful/tender” and “swollen”.

Any intra-articular injection (baseline and post baseline) sets the joint status to “painful/tender” and “swollen” - on or after the date of the injection.

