Tender/Painful Joint Count (68)	X	X		X		X		X		X	X	
Swollen Joint Count (66)	X	X		X		X		X		X	X	
Patient Assessment of Arthritis Pain (PAAP) VAS		X		X		X		X		X	X	
Patient Global Assessment (PtGA) of Arthritis VAS		X		X		X		X		X	X	
Physician Global Assessment (PhGA) of Arthritis ^f		X		X		X		X		X	X	
Health Assessment Questionnaire – Disability Index (HAQ-DI)		X		X		X		X		X	X	
SF-36 Version 2 (Acute)		X						X		X	X	
FACIT-Fatigue		X						X		X	X	
EQ-5D-3L		X						X		X	X	
Log into IRT system	X	X	X	X		X				X	X	
Investigational Product Dispensing		X	X ^w	X		X						
Randomization (after all screening procedures are complete and reviewed) ^s		X										

090177e190fc2bd0Approved\Approved On: 27-May-2019 05:59 (GMT)

Protocol Activity	Screening	Treatment Period								FU	FU/EOS	EW ^b
Visit Identifier	1	2	3	4	5	6	7	8	9	10		
Study Day/Week ^a	Days -28 to 0	Week 0	Week 1	Week 4	Week 6	Week 8	Week 10	Week 12	Week 14	Week 16		
		Day 1/ Baseline	Day 8	Day 29	Day 43	Day 57	Day 71	Day 85	Day 99	Day 113		
Visit Window	Days -28 to 0	±2 Days based on Week 0/Day 1 visit										
Administration of PF-06650833, Placebo or Tofacitinib ^t		X	X	X	X	X	X	X				
Review of subject diary (review of subject dosing record), IP accountability and compliance check throughout the study ^u		X	X	X	X	X	X	X			X	
Dispensing of subject diary		X	X	X	X	X	X					
Serious and non-serious adverse event monitoring	X	→	→	→	→	→	→	→	→	X	X	
Prior/Concomitant Medication & Treatments		X	→	→	→	→	→	→	→	X	X	
Discharge from the study										X	X	

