7.1. Efficacy Assessments

7.1.1. American College of Rheumatology (ACR) Assessments

The specific components of the ACR Assessments (ACR Core Dataset) that will be used in this study are:

1. Tender/Painful Joint count (TJC) (68).
2. Swollen Joint Count (SJC) (66).
3. Patient's Assessment of Arthritis Pain.
4. Patient's Global Assessment of Arthritis.
5. Physician's Global Assessment of Arthritis.

6. C-Reactive Protein (CRP), measured by high sensitivity methodology (hsCRP).
7. Erythrocyte Sedimentation Rate (ESR).
8. Health Assessment Questionnaire – Disability Index (HAQ-DI).

Components of the ACR Core Dataset will be collected at the visits indicated in the [Schedule of Activities](#) and [Section 6](#).

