7.1.5. Composite Efficacy Assessments Derived from the ACR Core Dataset

7.1.5.1. Simplified Disease Activity Index (SDAI) Assessment

The SDAI is a continuous composite measure derived components of the ACR Core Dataset. The SDAI will be calculated using the following formula:

$SDAI = TJC \text{ (using 28 joints)} + SJC \text{ (using 28 joints)} + PtGA \text{ (0–10 cm scale)} + PhGA \text{ (0–10 cm scale)} + \text{and hsCRP (mg/dL)}$.

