7.1.5.2. ACR Responder Analysis

The American College of Rheumatology's definition for calculating improvement in RA (ACR20) is calculated as a 20% improvement in tender and swollen joint counts and 20% improvement in 3 of the 5 remaining ACR-core set measures: patient and physician global assessments, pain, disability, and an acute-phase reactant which for this study will be CRP. Similarly, ACR50 and ACR70 are calculated with the respective percent improvement. Components of the ACR Responder Index will be collected as indicated in the [Schedule of Activities](#).

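### SAP Appendix 3 derives ACR20/50/70 from 28-joint counts and an open choice of ESR or CRP, while the protocol's ACR definition uses the 68/66-joint core set and CRP; the change is not declared

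*SAP*

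**What the plan says.** ACR20, ACR50 and ACR70 responder rates at Weeks 4, 8 and 12 are secondary endpoints (protocol 2.5, SAP 3.2). They are also one of the three efficacy summaries that SAP Section 3 gives for the tofacitinib arm.

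**Protocol.** Section 7.1.1 lists the components of the ACR core dataset for this study. The first is "Tender/Painful Joint count (TJC) (68" joints and the second is the 66-joint swollen count. Section 7.1.5.2 defines ACR20 as 20% improvement in the tender and swollen counts and in three of the five other core-set measures, the last of these being "an acute-phase reactant which for this study will be CRP". ACR50 and ACR70 use the same components.

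**SAP.** Appendix 3 gives the working definition. The tender criterion is "A 20% improvement from baseline in the tender/painful joint count (TCJ28" (TCJ28 is evidently TJC28), the swollen criterion uses SJC28, and the fifth of the remaining items is "Results of ESR or CRP blood test (both of which test for inflammation". ACR50 and ACR70 are defined in the same way. SAP 6.2.3 gives the analysis of the ACR rates but no other derivation.

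**The concern.** The SAP appendix is what programmers will follow, and it differs from the protocol in two ways.

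- The joint counts are the 28-joint versions rather than the 68/66 versions.
- The acute-phase reactant is left open, although the protocol settled it.

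Rates produced this way and reported as ACR20/50/70 would not be the protocol's endpoint. Two programmers working from the same text could also differ, by using CRP, using ESR, or counting the item as met when either improves. A further gap follows from the 28-joint basis: inclusion criterion 7 asks for at least 6 tender and 6 swollen joints but does not require them to lie within the 28-joint set. A 28-joint baseline of zero is therefore possible, and percent improvement is then undefined.

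**Working it through.** The documents state no ACR response rate, so there is no planned figure to reproduce. The check compares the texts and then asks whether the two definitions can disagree.

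**1. The texts side by side**

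| Element | Protocol 7.1.1 and 7.1.5.2 | SAP Appendix 3 |
|---|---|---|
| Tender joints | 68 | 28 |
| Swollen joints | 66 | 28 |
| Acute-phase reactant | CRP | ESR or CRP, no selection rule |

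Section 7.1.5.2 speaks of the tender and swollen counts and then of the five remaining core-set measures. The counts it means are therefore those in the core set, which 7.1.1 gives as 68 and 66. Where the protocol wants 28 joints it says so: the SDAI formula in 7.1.5.1 has "using 28 joints" against both counts, and 7.1.6 says the same of DAS28.

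**2. Joints left out:** 68 − 28 = 40 tender and 66 − 28 = 38 swollen.

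**3. Can the joint criterion differ?** Improvement = 100 × (baseline − Week 12) / baseline. Both patients are hypothetical.

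| | Tender, 28 joints | Tender, 68 joints | Swollen, 28 joints | Swollen, 66 joints |
|---|---|---|---|---|
| A | 10 to 7: 30% | 20 to 17: 15% | 8 to 6: 25% | 16 to 14: 12.5% |
| B | 10 to 9: 10% | 20 to 14: 30% | 8 to 7: 12.5% | 16 to 12: 25% |

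Patient A meets the 20% joint criteria under the SAP and fails them under the protocol; patient B does the reverse.

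**4. Can the reactant matter?** Take a patient who meets the joint criteria and exactly two of the other four items. CRP falling from 10 to 9 mg/L is 10% and fails; ESR falling from 40 to 30 mm/h is 25% and passes. ACR20 status then depends on which test is read. The Schedule of Activities has both tests at baseline and Weeks 4, 8 and 12, so the choice is a live one.

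**5. Zero 28-joint baseline.** With 6 tender joints spread evenly over 68, P(none in the 28-set) = C(40,6)/C(68,6) = 3,838,380/109,453,344 = 3.5%. If joints in the 28-set are twice as likely to be involved, drawing one joint at a time gives (40/96)(39/95)(38/94)(37/93)(36/92)(35/91) = 0.4%; at three times as likely it is 0.1%. With 10 tender joints it is at most 0.3%. The joint spread is an assumption.

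**6. Scale at the level of ACR response, on assumed inputs only.** The full rule was simulated over 216 scenarios of 40,000 patients each. The assumptions were:

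- mean tender/swollen counts of 15/10, 20/13 or 25/16, with the entry minimum of 6;
- 28-set joints 1 to 3 times as likely to be involved;
- mean joint persistence 0.25 to 0.6, and a new-joint rate of 0 or 0.03;
- loading of the other items on the latent response of 0.3 or 0.7;
- log-change SD 0.75 for CRP and 0.45 for ESR, with residual correlation 0.3 or 0.7.

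Under the protocol's rule ACR20 ran from 24% to 76%.

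| Switch from 68/66 to 28/28 | Patients whose status changes, median (range) |
|---|---|
| ACR20 | 5.6% (0.8% to 16%) |
| ACR50 | 1.8% (0.6% to 8%) |
| ACR70 | 0.2% (0% to 1.9%) |

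Changes went both ways, and the net shift in the ACR20 rate was −8.2 to +0.2 points. Counting either reactant as sufficient raised ACR20 by 0.7 to 4.1 points and ACR50 by 0.1 to 2.1 points. For scale, 5.6% of 30 to 36 patients is 1.7 to 2.0 patients, and one patient moves an arm's rate by 1/36 to 1/30, or 2.8 to 3.3 points.

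**The case against.** The best defence is that the SAP was entitled to do this. Protocol 9.2.1 leaves secondary-endpoint analyses to the SAP, and both documents let the SAP modify the plan, asking for a protocol amendment only for major changes to the primary endpoint. The SAP also labels its separate joint-count endpoint as 28-joint in 3.2, 6.2.5 and Appendix 1, which suggests a convention. Section 7.1.5.2 does not itself repeat 68 and 66, and the SDAI, also derived from the core dataset, uses 28 joints. Finally, the SAP says it is based on the protocol, so ESR or CRP could simply be read as CRP.

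Part of this stands:

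- The authority to modify is real, and no amendment was needed.
- Only the CRP conflict is express; the 68/66 basis comes from reading 7.1.5.2 with 7.1.1.
- The sentence in 7.1.5.2 that "Components of the ACR Responder Index will be collected as indicated in the" Schedule of Activities does not settle the count, because 7.1.6 says the same of the DAS components and 7.1.3.1 derives the 28-joint counts from the collected 68/66.
- SAP Table 1 logs changes between SAP versions, so its silence proves little by itself.
- A zero baseline could be handled as missing under SAP 5.3.1, although the SAP does not say that an undefined percentage counts as missing.
- The simulation does not estimate anything about this trial.

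None of it removes the point. A power to modify is not a statement that a modification was made, and no SAP section identifies or justifies one. A 28-joint label on a different endpoint does not redefine ACR. If the reader must go back to the protocol to learn which reactant applies, the SAP's derivation rule is incomplete.

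**Conclusion.** The concern holds. The reactant wording contradicts an explicit protocol choice. The joint-count basis contradicts the protocol when 7.1.5.2 is read with 7.1.1. Both conclusions rest on the texts alone, and the worked patients show that the definitions can classify one person differently in either direction.

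How often that would happen here cannot be derived from the documents, and the simulated rates only show a plausible order of magnitude. The consequence is confined to the ACR rates: SDAI, the sample size and the futility rule do not use them, and no effect on drug–placebo differences is claimed. This should be corrected, but it does not threaten the primary analysis.

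**What to change.** In SAP Appendix 3, define ACR20/50/70 on TJC68 and SJC66, with CRP as the only acute-phase reactant. Leave the 28-joint counts for SDAI, DAS28 and the SAP's own 28-joint change-from-baseline endpoint. The missing-joint rules in Appendix 3 work joint by joint and carry over.

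If a 28-joint ACR is wanted as well, add it as a declared supplementary analysis, record it in SAP Table 1, keep CRP as the reactant, and state how a zero baseline count is handled. Either change should be settled before unblinding.

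The cost is SAP wording and derivation code. The 68 and 66 counts and hsCRP are already collected at baseline and Weeks 4, 8 and 12.

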The secondary and sensitivity analysis will also include: ANCOVA models adjusting for SDAI baseline value, nominal treatment indicator, TNF exposure status (models including geography or country effect will also be considered). Fitting parametric monotone models for dose - response estimation after conducting Bayesian predictive checks on monotonicity (3 and 4 parameter E_{\max} models, semiparametric models based on spline fitting); advanced data visualization techniques for statistical results presentations. This will include multivariate parallel coordinate plots representing each patient response across set of variables, correlation plots, density estimates for SDAI score, box-plots for SDAI and DAS score changes. Model fitting will be conducted using model discrimination approach based on AIC and BIC criteria as well as visual assessment of fit and residuals.

Missing values due to a patient dropping from the study for lack of efficacy or adverse event, will be handled by setting the SDAI score to nonresponsive (baseline observation carried forward, BOCF).

Missing values that occur while the patient is still enrolled (eg, due to a protocol deviation where the data were not collected), will be handled by the method of last observation carried forward (LOCF). The most recent data on each SDAI domain will be used for calculating the missing SDAI score.

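### SAP Appendix 3's missing-joint rule has no upper limit: read literally, a joint examination not done at Week 12 scores 56 SDAI points, where protocol 9.2 carries the last counts forward

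*SAP*

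**What the plan says.** SAP Appendix 3, under its heading on missing joint counts, gives opposite rules before and after the start of treatment for "A missing painful/tender assessment or one NOT DONE". At baseline: "A missing painful/tender assessment or one NOT DONE at *baseline* is set to “not painful/tender". Afterwards: "A missing painful/tender assessment or one NOT DONE *post baseline* is set to “painful/tender". The swelling rules mirror these ("A missing swollen assessment or one NOT DONE at *baseline* is set to “not swollen" and "A missing swollen assessment or one NOT DONE at *post baseline* is set to “swollen"). A further line treats a joint that becomes non-assessable during the trial in the same way: "Any *new* NOT APPLICABLE for a joint POST BASELINE is set to" tender and swollen. Joints already coded as not applicable are left out of the counts at all visits. No maximum number of missing joints is given.

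Appendix 3 derives ACR and DAS28 and does not mention SDAI. Protocol 7.1.5.1 defines SDAI as the plain sum of the 28-joint tender count, the 28-joint swollen count, two global scores on 0–10 scales and hsCRP in mg/dL. Neither document gives another derivation of the joint counts when joints are missing.

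Protocol 9.2 has its own rule for data not collected while a patient is still enrolled. It uses LOCF, applied by component: "The most recent data on each SDAI domain will be used for calculating the missing SDAI score".

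The SAP lists observed-case and LOCF handling for the sensitivity ANCOVAs of SDAI (sections 5.3.2 and 6.1.2, Appendix 1) and no imputation for the MMRM analyses of SDAI, DAS28 and joint counts (section 6.2). For the primary Bayesian analysis, the missing-data column of Appendix 1 holds only a dash.

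**The concern.** The joint counts can contribute up to 56 SDAI points, against 20 for the two global scores, so a rule that fills in joints acts directly on the primary endpoint. Three problems follow.

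- A joint with no observation at either visit is scored as a change.
- With no limit on missing joints, the rule still returns a number when nothing was examined. A joint count at an attended visit can then never be missing, so neither protocol 9.2's carry-forward nor the SAP's observed-case and LOCF options could act on the two joint domains. Results labelled as observed would contain worst-case imputed joints.
- Nothing says which rule takes precedence in the primary analysis. Protocol section 9 and SAP section 2 both say that a major change to the primary endpoint or its analysis will also be reflected in a protocol amendment. Protocol 9.2 contains no joint-level rule.

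The situation can arise. Not done is one of the recorded joint codes (Protocol 7.1.2 and 7.1.3). Joints are examined by an independent assessor with no other task (Protocol 7.9), while the global scores come from the patient and the investigator, and hsCRP from the central laboratory. A visit can therefore yield every SDAI component except the joints.

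**Working it through.** **Inputs from the documents.** Each tender joint and each swollen joint counts 1 point, over 28 joints, so 2 points per joint and at most 56 (Protocol 7.1.5.1). Planned completers are 36, 36, 36 and 30 on the four doses and 30 on placebo (Protocol 9.1), so 3×36 + 2×30 = 168 in the primary comparison. The plan states no figure of its own for this rule: no missing-joint rate and no SDAI standard deviation. Those used below are assumptions.

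**One joint, one count.** Change scored by Appendix 3, against carrying the baseline state forward:

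| Baseline | Week 12 | Appendix 3 | Carry-forward |
|---|---|---|---|
| clear | not done | +1 | 0 |
| active | not done | 0 | 0 |
| not done | clear | 0 | undefined |
| not done | active | +1 | undefined |
| not done | not done | +1 | undefined |

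A joint unassessed for both tenderness and swelling at both visits adds 2 points; four such joints add 8. For k joints not done at Week 12 only, with a share r active when last seen, Appendix 3 exceeds carry-forward by 2k(1−r). With k = 2 this is 4, 3, 2 and 0 points at r = 0, 0.25, 0.5 and 1.

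**Whole examination not done at Week 12.** Appendix 3 read literally gives 28 + 28 = 56. Change in the joint part of SDAI, for assumed tender/swollen counts:

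| Baseline | Last observed | Protocol 9.2 | Appendix 3 | Gap |
|---|---|---|---|---|
| 6/6 | 3/3 | −6 | +44 | 50 |
| 12/9 | 6/4 | −11 | +35 | 46 |
| 16/12 | 6/4 | −18 | +28 | 46 |
| 20/16 | 10/8 | −18 | +20 | 38 |

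**Effect on an arm.** One such subject among 36 shifts the mean by 38/36 = 1.1 to 50/36 = 1.4 points. The contrast with placebo moves equally if placebo has no such subject. If placebo has one among 30, it moves by 38×(1/36 − 1/30) = −0.2 to 50×(1/36 − 1/30) = −0.3.

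Measured against the true joint total instead, assumed totals of 20 down to 8 give an excess of 56−20 = 36 to 56−8 = 48 points. The arm mean then moves by 1.0 to 1.3 (n = 36) or 1.2 to 1.6 (n = 30). With an assumed residual SD of 12 and 168−5 = 163 degrees of freedom, the SD becomes √(144 + J²(1−1/36)/163), which is 12.3 at J = 36 and 12.6 at J = 48.

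**Scattered joints.** If a fraction m of joints is not done at Week 12, the expected excess is 28m[(1−p_tender) + (1−p_swollen)].

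| m | Responding arm (20% tender, 14% swollen) | Poorly responding arm (40%, 28%) | Difference = 28m×0.34 |
|---|---|---|---|
| 1% | 0.46 | 0.37 | 0.10 |
| 2% | 0.93 | 0.74 | 0.19 |
| 5% | 2.32 | 1.85 | 0.48 |

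The last column is what reaches the placebo-adjusted effect when missingness is equal across arms.

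**The case against.** The strongest reply is that the two rules work at different levels. Protocol 9.2 carries forward a whole domain and says nothing about a single unassessed joint in an otherwise completed count. The Appendix 3 bullets match the per-joint codes and can be read as filling that gap, and the protocol allows the SAP to modify its plans. On that reading a wholly undone examination stays missing, the SAP's observed-case and LOCF options keep their meaning, and no subject is scored 56. Artificial or absent joints, an obvious reason for non-assessment at both visits, are coded not applicable and carry no penalty. Worst-case scoring also fits the conservative handling elsewhere: BOCF in the protocol and non-responder imputation in the SAP.

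Much of this stands. For a few missing joints there is a gap rather than a conflict, and the reach to SDAI is an inference from the shared counts. But the reading that avoids 56 points is not written down. The heading refers to joint counts, no minimum is set, no order of precedence is given, and the primary analysis names no missing-data rule. A programmer following the text literally would produce the extreme value. The conservatism argument also does not cover joints unassessed at baseline, where scoring them clear and later active creates a change that was never observed.

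**Conclusion.** The concern holds in a limited form. Appendix 3 scores missing joints asymmetrically, without a limit on their number and without saying whether SDAI is covered. The direct conflict with protocol 9.2 is confined to examinations wholly or mostly not done, where the two rules differ by 38 to 50 points per subject in the assumed cases. The primary model assumes normal errors, so such values are not downweighted. The main harm is therefore outliers and added variance in arms of 30 to 36. Net bias from scattered joints is about 0.1 to 0.5 points between a responding and a poorly responding arm at 1% to 5% missing. Those rates, the activity shares and the SD are assumptions; actual impact is unknown.

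Three stronger readings are not supported:

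- A reader might infer that the SAP contradicts the protocol for every missing joint. The protocol is silent on single joints in a completed count.
- A reader might infer that all absent data become worsening. A joint active at baseline and unassessed later scores no change, as does one unassessed at baseline and clear later.
- A reader might infer that the rule works materially against effective doses. It is the same in every arm, and most of the shift cancels unless missingness, or the state of the missing joints, differs between arms.

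**What to change.** In SAP Appendix 3:

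- Limit the joint-level rule to partly completed counts with a stated minimum number of assessed joints, for example half. Treat a count below the minimum as missing and apply protocol 9.2's domain carry-forward. With a minimum of 14 assessed joints, at most 14 can be filled in, so the inflation is capped at 2×14 = 28 points; a higher minimum lowers this further.
- For SDAI and DAS28, leave a joint not assessed at baseline out of both visits and prorate the count to 28.
- State that these rules govern SDAI in the primary Bayesian analysis, and replace the dash in Appendix 1 with the rule that applies.
- Add a sensitivity analysis with carried-forward or prorated joints.

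The cost is SAP wording and derivation code, since joint-level data are already collected. The downside is scoring that is slightly less conservative than worst case.
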